9.2.2.3. Adverse Events of Special Interest

The following adverse events of special interest (AESIs) will be evaluated specifically to determine the safety and tolerability of ixekizumab over the range of doses selected for this clinical study.

AESIs for ixekizumab are:

- cytopenias (leukopenia, neutropenia, and thrombocytopenia),
- liver biochemical test changes/enzyme elevations (ALT, AST, bilirubin, and ALP),
- infections,
- immunogenicity,
- injection-site reactions,
- allergic reactions/hypersensitivities,
- cerebrocardiovascular events,
- malignancies,
- depression,
- inflammatory bowel disease, and

- interstitial lung disease.

If infections, injection-site reactions, or allergic/hypersensitivity reactions are reported, study sites will provide details on these events as instructed on the eCRF. Investigators will also educate participants and/or caregivers about the symptoms of allergic/hypersensitivity reactions and will provide instructions on dealing with these reactions. A blood sample will be collected when possible for any participant who experiences an AE of allergic reactions/hypersensitivities during the study.

In the case of suspected IBD, the participant should be referred to a gastroenterologist (preferably pediatric gastroenterologist) for evaluation and management. Data on suspected IBD, as identified by events possibly indicative of ulcerative colitis or Crohn's disease will be collected, and the events will be adjudicated by an external Clinical Events Committee (CEC) composed of gastroenterologists with expertise in IBD. The role of the CEC is to adjudicate defined clinical events in a consistent, and unbiased manner throughout a study. The importance of the CEC is to ensure that all events that have been reported are evaluated uniformly by a single group.

9.2.3. *Complaint Handling*

Lilly collects product complaints on investigational products and drug delivery systems used in clinical studies in order to ensure the safety of study participants, monitor quality, and to facilitate process and product improvements.

Participants will be instructed to contact the investigator as soon as possible if he or she has a complaint or problem with the investigational product so that the situation can be assessed.

9.3. *Treatment of Overdose*

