10.3.4.1. Adverse Events

Adverse events are considered TEAEs if they first occur or worsen after the start of treatment during a study period. In the case of a missing onset date for an AE, an AE with a start date equal to or greater than the dosing date will be considered a TEAE. For each TEAE, the severity is recorded according to the participant's or physician's perceived severity of the event (mild, moderate, or severe).

Treatment-emergent adverse events, SAEs including deaths, AEs that lead to investigational product discontinuation, and AEs by maximum severity and relationship to investigational product will be summarized by the Medical Dictionary for Regulatory Activities System Organ Class (SOC) and Preferred Term (PT). Treatment-emergent adverse events will also be summarized by PT sorted by decreasing frequency within SOC for all TEAEs, TEAEs by maximum severity, and TEAEs considered possibly related to study drug. For events that are gender specific, the denominator and computation of the percentage will include only participants from the given gender.

Medical Dictionary for Regulatory Activities groupings of PTs will be used to investigate AESIs.

Adverse events of special interest will also be presented by severity. Adverse events of special interest will include cytopenias, liver function test changes/enzyme elevations, infections, immunogenicity, injection site reactions, allergic/hypersensitivity reactions, cerebrocardiovascular events, malignancies, depression, IBD, and interstitial lung disease.

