6.12.2. Adverse Events

6.12.2.1. Analysis of Adverse Events

Adverse events are classified based on MedDRA. A TEAE is defined as an event that first occurred or worsened in severity after baseline and on or prior to the date of the last visit within the treatment period. Both the date/time of the event and the date/time of the dose (that is, injection) are considered when determining TEAEs. The MedDRA Lowest Level Term (LLT) will be used in the treatment-emergent computation. The maximum severity for each LLT during the baseline period will be used as baseline severity (in some cases baseline period is a single time point). Events with a missing severity during the treatment period will be considered treatment emergent. The treatment period will be included as post-baseline for the analysis. If an event is pre-existing during the baseline period but it has missing severity, and the event persists during the treatment period, then it will be considered as treatment-emergent, regardless of the post-baseline level of severity. Adverse events with a particular LLT will be classified as treatment-emergent if they first start on or after the first dose date in the treatment period (i.e., a

patient has no pre-existing conditions with that LLT), or if the severity is greater than the pre-treatment severity for that LLT.

A follow-up emergent adverse event (FEAE) is defined as an event that first occurred or worsened in severity after the date of Week 104 (Visit 29) or the ETV. The MedDRA LLT will be used when classifying FAEs as follow-up emergent. For AEs that are ongoing at the date of Week 104 (Visit 29) or ETV, the maximum severity recorded for each LLT on the date of Week 104 (Visit 29) or ETV will be used as the follow-up baseline severity for that lowest level term.

An overview table will be provided and will include the frequency and percentage of patients who experienced a TEAE, TEAE by maximum severity, a treatment-emergent AESI, SAE, died, or discontinued from the study due to an AE (including death) will be summarized by treatment group for each treatment period. A listing will be provided as well.

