6.12.11. Special Safety Topics

Safety information on special topics including AESI will be presented by treatment group and by study period. [Table RHCG.6.16](#) provides the definitions/derivations and analyses methods (including analyses, summaries and by-patient listings) of special safety topics including AESIs.

Potential AESIs will be identified by a standardized MedDRA query (SMQ) or a Lilly-defined MedDRA PT listing. Preferred terms within an SMQ will be classified as broad and narrow. In the Lilly-defined MedDRA PT listings, Lilly has provided the broad and narrow classification. The Lilly-defined broad terms are for a more sensitive search of potential events of interest and the Lilly-defined narrow terms are for a more specific search. Therefore, the summaries will include the classifications of broad term (same as pooling narrow and broad terms together) and narrow term. In the event that the listing of terms or analysis changes for a special safety topic, it will be documented in the program safety analysis plan (PSAP) which will supersede this document; it will not warrant an amendment to the individual study SAP.

Table RHCG.6.16. Definitions and Analyses of Special Safety Topics

Special Safety Topic	Definition / Derivation	Analysis / Summary / Listing

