	
[4] Clear bump 2 mm thick or more
 
Pain (including burning) (Scored 0-3)
 
 [0] None [1] Mild [2] Moderate [3] Severe 	
OLT Period (Safety Population): TEAE by maximum severity TEAE by maximum redness category TEAE by maximum swelling category TEAE by maximum pain category
 
OLE Period (OLE Period Population): TEAE by maximum severity TEAE by maximum redness category TEAE by maximum swelling category TEAE by maximum pain category
 
LTE Period (LTE Safety Population): TEAE by maximum severity TEAE by maximum redness category TEAE by maximum swelling category TEAE by maximum pain category

Malignancies	
Malignancies will be defined using PTs from the Malignant or unspecified tumors SMQ as defined in MedDRA (SMQ: 20000091, which includes the sub-SMQs:
 
 • 20000194 [Malignant tumours], including sub-SMQs of 20000227 [Haematological malignant tumours] and 20000228 [Non-haematological malignant tumours] • 20000195 [Tumours of unspecified malignancy], including sub-SMQs of 20000229 [Haematological tumours of unspecified malignancy] and 20000230 [Non-haematological tumours of unspecified malignancy] 
The number and percentage of patients with TEAEs will be summarized by treatment group using MedDRA PT nested within the following categories:
 
 • Non-Melanoma Skin Cancer (NMSC) 
 ◦ Basal Cell Carcinoma, 
 ▪ PTs include: Basal cell carcinoma, Basosquamous carcinoma, and Basosquamous carcinoma of skin 	
OLT Period (Safety Population): TEAE by PT within Category
 
OLE Period (OLE Period Population): TEAE by PT within Category
 
LTE Period (LTE Safety Population): TEAE by maximum severity TEAE by maximum redness category TEAE by maximum swelling category TEAE by maximum pain category

Special Safety Topic	Definition / Derivation	Analysis / Summary / Listing
	
 ○ Squamous Cell Carcinoma: 
 ▪ PT: Squamous cell carcinoma of skin, Bowen's disease, Lip squamous cell carcinoma, Skin squamous cell carcinoma metastatic, and Keratoacanthoma ● Malignancies excluding NMSC: all PTs in the Malignant or unspecified tumors SMQ excluding the 8 defined NMSC PTs. 	Listing (Safety Population): TEAE

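### SAP Table RHCG.6.16 gives no grouping or display for cerebrocardiovascular events, one of the protocol's 11 AESIs, and its Malignancies row contradicts itself for the LTE period

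*SAP*

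**What the plan says.** Protocol 9.2.2.3 opens its list with "AESIs for ixekizumab are" and gives 11 topics. Protocol 10.3.4.1 repeats the list, which ends with "cerebrocardiovascular events, malignancies, depression, IBD, and interstitial lung disease". The same section sets two requirements: "Medical Dictionary for Regulatory Activities groupings of PTs will be used to investigate AESIs" and "Adverse events of special interest will also be presented by severity".

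SAP 6.12.11 hands the implementation to Table RHCG.6.16, which it says "provides the definitions/derivations and analyses methods (including analyses, summaries and by-patient listings) of special safety topics including AESIs". SAP 6.12.2.1 plans an overview table, by treatment group and period, that counts patients with "a treatment-emergent AESI, SAE, died, or discontinued from the study due to an AE".

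In the Malignancies row of that table, the definition column asks for patients with TEAEs by preferred term nested within two categories, non-melanoma skin cancer and all other malignancies, and names no period. The display column follows this for the open-label treatment (OLT) and open-label extension (OLE) periods. For the LTE it lists maximum severity, "TEAE by maximum redness category", and the matching swelling and pain displays. The redness phrase also stands, correctly, three times in the Injection Site Reactions row above. Only its occurrence under Malignancies is at issue.

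**The concern.** AESIs, with AEs and SAEs, form a named secondary endpoint of the LTE (Protocol Section 4; SAP 4.2), and the overview table counts them in each period. An AESI with no term list cannot be counted there under a rule fixed in advance. Someone would have to choose the terms later, in an open-label study whose data are already visible.

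The malignancy cell is a different kind of fault. A programmer working from the display column would produce three displays with no meaning for a malignancy and leave out the one that is needed. This would happen in the longest treatment period, Week 104 to Week 264 (264 − 104 = 160 weeks).

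**Working it through.** No power, alpha or event figure is involved. The check is a one-to-one match of topics, then a comparison of displays by period.

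**Step 1. Protocol AESIs against the SAP.**

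| Protocol AESI | Place in the SAP |
|---|---|
| Cytopenias | Table RHCG.6.16, also 6.12.4 and 6.12.4.1 |
| Liver test changes/enzyme elevations | Table RHCG.6.16 (Hepatic) |
| Infections | Table RHCG.6.16 |
| Immunogenicity | 6.12.12 |
| Injection-site reactions | Table RHCG.6.16 |
| Allergic reactions/hypersensitivities | Table RHCG.6.16 |
| Cerebrocardiovascular events | none |
| Malignancies | Table RHCG.6.16 |
| Depression | Table RHCG.6.16 (with suicide/self-injury) |
| Inflammatory bowel disease | Table RHCG.6.16 |
| Interstitial lung disease | Table RHCG.6.16 |

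Nine table rows plus one separate section cover 10 topics, and 11 − 10 = 1 is left. None of the nine SAP appendices supplies a cerebrocardiovascular term list.

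**Step 2. Is the row merely missing from the copy?** The SAP contents list puts Table RHCG.6.16 on page 86 and 6.12.12 on page 96, which leaves ten pages. The table's column header appears ten times, and the table carries no redaction mark. Nothing suggests a lost or blacked-out row.

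**Step 3. Displays by period.**

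| Row | OLT | OLE | LTE |
|---|---|---|---|
| Injection Site Reactions, second block | severity, redness, swelling, pain | same | same |
| Malignancies | TEAE by preferred term within category | same | severity, redness, swelling, pain |
| Interstitial Lung Disease | TEAE by preferred term within category | same | same |

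The Malignancies LTE cell matches the injection-site LTE cell item for item. Redness, swelling and pain are the scores set out with the Injection Site Reaction eCRF page, so three of the cell's four displays cannot apply. The fourth, maximum severity, can. The preferred-term-within-category table is absent from the cell. The SAP revision history records that LTE details were added throughout 6.12, which fits a copying slip.

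**The case against.** Several points on the other side are sound.

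- **The events are not lost.** SAP 6.12.2.1 plans TEAE tables for all three periods by system organ class and preferred term, by preferred term alone, and by maximum severity; SAEs are tabulated in 6.12.3.2. This stands. What is missing is the defined grouping and its severity display.
- **A program safety analysis plan may override the SAP.** SAP 6.12.11 allows this when the term list or analysis for a special topic changes, and SAP 6.12 refers to compound-level standards. Neither document is available here. The clause covers changes to topics. It does not say that a topic absent from the table is defined elsewhere.
- **The consequence is limited.** Protocol 3.3 states that trial data do not suggest an association between ixekizumab and cerebrocardiovascular events or malignancies, and at least 100 participants are planned. Events may be few. The protocol still designates both as AESIs.

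A reader might infer that Table RHCG.6.16 is the SAP's only definition of AESIs. It is not, because immunogenicity is defined and analysed in 6.12.12.

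A reader might also infer that the LTE has no malignancy tabulation, so that two AESIs go untabulated. The documents do not support that. The definition column calls for the preferred-term summary without limiting the period, SAP 6.12.11 says special topics are presented by study period, the LTE cell keeps maximum severity, and a TEAE listing is planned. The row contradicts itself; the analysis has not been removed.

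**Conclusion.** The point holds in two parts of unequal weight. The main one is that the SAP implements 10 of the protocol's 11 AESIs and gives cerebrocardiovascular events no MedDRA grouping or display in OLT, OLE or LTE. They cannot be counted in a pre-specified way in the overview's AESI line or shown by severity as a group. The SAP does not say that this line is restricted to the table's topics, so it would go too far to say that such events will certainly be left out of it. What is certain is that no rule for including them is given.

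The lesser part is an internal inconsistency in one cell: the Malignancies LTE entry has three inapplicable displays and lacks one that its own definition column requires.

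Neither part touches the primary analysis, the sample size or a decision rule. The conclusion assumes that no program-level plan already defines the cerebrocardiovascular grouping for this study. If one does, the SAP should cite it.

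**What to change.** 1. Add a cerebrocardiovascular row to Table RHCG.6.16 with its MedDRA term grouping. For OLT, OLE and LTE, specify TEAEs by preferred term and by maximum severity, plus a by-patient listing.
2. In the Malignancies LTE cell, remove the redness, swelling and pain displays, add TEAEs by preferred term within category, and keep TEAEs by maximum severity. Simply copying the OLT or OLE entry into the cell would delete the severity display, which Protocol 10.3.4.1 asks for.

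The cost is two edits to one SAP table and the programming of the added displays. No protocol change or new data collection is needed.

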6.12.12. Immunogenicity

6.12.12.1. Definitions and Terms

[figure not shown]
The following sample- and patient-related definitions and parameters will be used to describe the immunogenicity data.

6.12.12.1.1. Sample Category Definitions

Samples are classified into the following categories:

- **Unevaluable sample:** Sample could not be tested for ADA due to sample loss, mishandling, or errors in collection, processing, storage, and so on.
- **Anti-drug antibody- (ADA-) Positive sample:** The presence of ADA is detected and confirmed. The samples are reported as positive. If the sample is positive, a titer value is reported.
- **Neutralizing anti-drug antibody- (NAb-) Positive sample:** NAb are reported as detected.
- **Anti-drug antibody (ADA-) Negative sample:** The presence of ADA is not detected and the assay drug tolerance level is not exceeded.
- **NAb-Negative sample:** The presence of NAb is not detected and the assay drug tolerance level is not exceeded.
- **NAb-Inconclusive:** A patient without a NAb positive sample and with at least 1 sample for which drug levels may interfere with the NAb assay.

Figure RHCG.6.1 illustrates the relationship of some of the above terms.

Abbreviation: ADA = anti-drug antibody.

Figure RHCG.6.1. Sample definitions.

6.12.12.1.2. Patient Category Definitions

The following categories are applied to patients, based on the classification of their samples:

- **Unevaluable patient:** a) a patient with no evaluable baseline sample and/or no evaluable postbaseline samples; b) a patient with an evaluable baseline sample, but no evaluable postbaseline sample; c) a patient with no evaluable baseline sample, but whose evaluable postbaseline values are all ADA-positive or a mix of positive and negative. Note: If all postbaseline samples are negative, the patient is considered “evaluable” and will be classified as ADA-negative.
- **Evaluable patient:** a) Patient with an evaluable baseline sample and at least 1 evaluable postbaseline sample (that is, sample after administration of study drug); b) patient with no evaluable baseline sample whose evaluable postbaseline samples are all ADA negative.

Figure RHCG.6.2 illustrates the relationship of the above terms.

[figure not shown]

Figure RHCG.6.2. Patient categories (evaluable/unevaluable) based on sample status at baseline and postbaseline.

[figure not shown]
6.12.12.1.3. Definitions for Clinical Interpretation of Assay Results

- **Baseline:** For immunogenicity analyses, baseline is the last nonmissing observation on, or prior to, the date of the first injection of study treatment of ixekizumab. For patients originally randomized to ixekizumab in the OLT period and for patients receiving adalimumab continuously throughout the OLT and OLE periods (i.e., never received

ixekizumab treatment), baseline is Week 0. For patients who first receive ixekizumab during the OLE period, baseline is the last nonmissing observation on, or prior to, the date of the first injection of ixekizumab.

- **Baseline ADA-positive (preexisting antibody):** ADA detected in a sample collected at baseline.
- **Baseline ADA-negative:** ADA is not detected in a sample collected at baseline.
- **Treatment-emergent- (TE-) ADA positive:** a) a patient with a ≥ 4 -fold increase over a positive baseline antibody titer; or b) for a negative baseline titer, a patient with an increase from the baseline to a level of $\geq 1:10$.
- **TE-ADA inconclusive:** A patient without a TE-ADA positive sample and with at least 1 sample for which drug levels may interfere with the ADA assay.
- **TE-ADA negative:** A patient who is evaluable for TE-ADA and is not either TE-ADA positive or TE-ADA inconclusive.

Figure RHCG.6.3 illustrates the relationship of some of these terms.

Abbreviation: ADA = anti-drug antibody.

Figure RHCG.6.3. Relationship of terms for clinical interpretation of assay results for evaluable patients.

- **Incidence of TE-ADA:** Patients with TE-ADA as a proportion of the evaluable patient population during the treatment and follow-up periods. This excludes unevaluable patients.

All ADA positive samples will be evaluated for NAb. Definitions for NAb patient status will be defined as follows:

- **NAb-positive:** A patient where a NAb positive result is detected for ≥ 1 TE-ADA positive samples.
- **NAb-inconclusive:** A patient without a NAb positive sample and with at least 1 sample for which drug levels may interfere with the NAb assay.

- **NAb-negative:** A patient who is evaluable for NAb and is not either NAb positive or NAb inconclusive.

A flow chart that reflects the connection between the analytical test results and the clinical interpretation based on the definitions is shown in [Figure RHCG.6.4](#).

[figure not shown]

Figure RHCG.6.4. Flow chart of ADA assessment with clinical interpretation of the various result possibilities.

6.12.12.2. Immunogenicity Analyses

Immunogenicity evaluable patients will be identified as TE-ADA positive, TE-ADA negative, or TE-ADA inconclusive, according to the definitions provided in Section [6.12.12.1.2](#) and further grouped into TE-ADA status groups and time-varying TE-ADA status groups:

TE-ADA Status Groups:

- TE-ADA status (positive, negative, or inconclusive)

- NAb status (positive, negative, or inconclusive) for TE-ADA positive patients
- TE-ADA titer groups for TE-ADA positive patients:
 - Low Titer: TE-ADA titer value (LOCF) $<1:160$
 - Moderate Titer: TE-ADA titer value (LOCF) $\geq 1:160$ and $<1:1280$
 - High Titer: TE-ADA titer value (LOCF) $\geq 1:1280$

Time-Varying TE-ADA Status Groups:

Individual ADA samples will be ascribed into 3 different dichotomous variables as explained in [Table RHCG.6.17](#). Each variable has possible values of a “greater-TE-ADA status” or a “lesser-TE-ADA status,” in the sense that the level of TE-ADA detected in the greater-TE-ADA category is higher than in the lesser-TE-ADA category.

Table RHCG.6.17. TE-ADA Status Dichotomous Variables for AE Analysis

TE-ADA Status Dichotomous Variable	Greater-TE-ADA Status	Lesser-TE-ADA Status
TE-ADA positive	TE-ADA positive	not TE-ADA positive
TE-ADA moderate-to-high	TE-ADA positive with moderate titer or high titer	not TE-ADA positive, or TE-ADA positive with low titer
TE-ADA high status	TE-ADA positive with high titer	not TE-ADA positive, or TE-ADA positive with low or moderate titer

Abbreviations: AE = adverse event; TE-ADA = treatment-emergent antidrug antibodies.

Note: For purpose of this analysis, TE-ADA Inconclusive is taken to be “not TE-ADA positive.” A TE-ADA low is defined as a TE-ADA positive with a titer value $<1:160$; a TE-ADA moderate is defined as a TE-ADA positive with a titer value $\geq 1:160$ and $<1:1280$; and a TE-ADA high is defined as a TE-ADA positive with a titer value $\geq 1:1280$.

For each TE-ADA status dichotomous variable, a time-varying TE-ADA status will be computed. At time t , the TE-ADA status is taken to be the highest of the TE-ADA values bracketing time t . More formally, the TE-ADA status at time t is given by the greater of: (a) the TE-ADA status at the most-recent postbaseline measurement prior to t ; and (b) the TE-ADA status at the first TE-ADA postbaseline measurement at or after time t . In this computation, “greater” is given by the greater-TE-ADA status of [Table RHCG.6.17](#). If there is no value satisfying criterion (a), then the value (b) is used. Similarly, if there is no value (b), then the value (a) is used.

For each TE-ADA status dichotomous variable, patients will be categorized according to whether they were: (1) always in lesser-TE-ADA status postbaseline; or (2) at some point postbaseline, were in greater-TE-ADA status.

